- g. All subjects with a positive PPD test or positive Interferon-Gamma Release Assay (IGRA; QuantiFERON-TB Gold In-Tube test or T-SPOT TB test) will undergo a standard CXR (posterior-anterior [PA] and lateral views) at the Screening Visit to rule out the presence of TB or other clinically relevant findings. The CXR will not be required if the subject had a previous normal chest x-ray within 90 days of Screening, provided all protocol required documentation is available at the site.
- h. For subjects with a negative TB test at Screening, TB test will be required at Week 52. If the annual TB screen is positive, a CXR may be required for evaluation of active TB. An annual TB screen testing will not be required for subjects who have been treated for latent or active TB or have had a positive TB test at any time (prior to the study, Screening, or testing performed at any time point during the study). For such subjects, annual evaluation by a physician for clinical signs/symptoms of active TB (including a directed TB history and physical exam including lungs, lymph nodes and skin) or newly identified TB risk factors will be required at Week 52.
- i. Subjects with normal ECG within 90 days of Screening would not require a repeat ECG, if documentation is available.
- j. Blood draws should be performed after completion of all clinical assessments and questionnaires.
- k. Lab assessments will only need to be repeated at Baseline if the time between Screening lab assessments and Baseline is greater than 28 days, or any new concomitant medication with potential impact on laboratory parameters was started during the Screening Period. For subjects in re-screening lab assessments will not need to be repeated if the time between Screening and Re-screening is less than or equal to 28 days. However, lab assessments will need to be repeated at Baseline if the time between lab assessments during previous Screening and Baseline is greater than 28 days.
- l. Dipstick urinalysis will be completed by the sites at all required visits. A microscopic analysis will be performed by the central laboratory, in the event the dipstick results show protein, ketones or blood greater than negative or glucose greater than normal.
- m. All females of childbearing potential will have a serum pregnancy test at Screening, and Week 52/Premature Discontinuation Visit.

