For subjects with a negative TB test at Screening, either an annual PPD or IGRA test will be required for any subject participating in the trial at Week 52 (Table 1). If the annual TB screen is positive (PPD is positive or the IGRA test is positive), a CXR may be required for evaluation of active TB. For any subject with a positive annual TB screen, the site should contact the AbbVie Medical Monitor for further discussion. Subjects found to have latent TB, will be required to start a course of CDC recommended prophylaxis or prophylaxis per local guidelines as soon as possible. Subjects found to

have active TB must discontinue study drug and receive CDC recommended or local guideline recommended treatment. Any positive TB screen after the subject has started the study, should be reported as an AE.

An annual TB screen with PPD or IGRA testing will not be required for subjects who have been treated for latent or active TB or have had a positive TB test (PPD or IGRA) at any time (prior to the study, Screening, annual evaluation, or testing performed at any time point during the study). For such subjects, annual evaluation by a physician for clinical signs/symptoms of active TB (including a directed TB history and physical exam including lungs, lymph nodes and skin) or newly identified TB risk factors will be required at Weeks 52 (Table 1). For any subject with clinical signs/symptoms of active TB or newly identified TB risk factors, a CXR may be required for evaluation of active TB, and it is recommended to contact the Medical Monitor for further guidance. Subjects with a confirmed active TB should be discontinued from the study and receive standard of care.

Chest X-ray (CXR)

All subjects with a positive PPD test or positive Interferon-Gamma Release Assay (IGRA; QuantiFERON-TB Gold In-Tube test or T-SPOT TB test) will undergo a standard CXR (posterior-anterior [PA] and lateral views) at the Screening Visit to rule out the presence of TB or other clinically relevant findings. In the event both a PPD test and IGRA test are performed, a CXR will only be required if the IGRA test is positive. The CXR will not be required if the subject had a previous normal chest x-ray within 90 days of Screening, provided all protocol required documentation is available at the site.

Subjects can have a repeat CXR at any time during the study as warranted based on the opinion of the Investigator.

Electrocardiogram (ECG)

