report will be monitored by the responsible CRA and kept with the subject's source documents onsite. Subjects would not be enrolled if colon dysplasia or colon cancer is discovered at Screening endoscopy. If a diagnosis of colon dysplasia or colon cancer or an infection is discovered during any subsequent endoscopic evaluation during the course of the study, the findings should be recorded as an adverse event and the subject should be discontinued from the study.

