8.1.5 Statistical Analyses of Safety

Adverse events (AEs), laboratory data and vital signs are the primary safety parameters in this study. All safety comparisons will be performed within the safety analysis set.

Treatment-emergent AEs are defined as new events that begin either on or after the first dose of the study medication and within 70 days after the last dose of the study medication.

Treatment-emergent adverse events (AEs) will be summarized by treatment group using descriptive statistics. AEs, including serious AEs, AEs of special interest such as AEs leading to death and AEs leading to premature discontinuation (see details in the SAP), will be tabulated by system organ class and preferred term whereby the most current implemented MedDRA dictionary will be used. Also, summaries by severity and relationship to study drug will be done.

Other safety variables like laboratory data will be described by descriptive statistics as mentioned before. In addition, shift tables and listings will be provided for abnormal values, whereby the normal range of the analyzing laboratory will be used.

Details of this and all other analyses will be provided in the SAP.

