9.1 Study Drug Exposure

Induction study drug exposure will be summarized for ITT, ITT-E and safety population by treatment groups defined in Section 5.1. The study drug exposure during induction period does not include the dose received at Week 8. The duration of exposure during induction period will be calculated as follows:

Duration of induction-exposure = last induction dose date - first induction dose date + (max.*) 14 days

*cutting before first dose of study drug in the maintenance period.

Maintenance study drug exposure will be summarized for mITT, mITT-E, RR and safety population (restricted to subjects who received at least one dose of the study drug during maintenance phase). Of note, patients in this study don't receive study drug at Week 52, unless they roll over into Study M10-870, then this will be their first dose of study drug in Study M10-870 (and will be documented in Study M10-870, not Study M11-290). The duration of exposure during maintenance will be calculated as follows:

Duration of maintenance-exposure = last maintenance dose date (prior to potential re-randomization due to 1st disease flare) – first maintenance dose date + (max.*) 14 days

*cutting before first dose of study drug after re-randomization due to 1st disease flare, if applicable, or the first dose of study drug in Study M10-870, if applicable.

[figure not shown]
ADA exposure after re-randomization due to 1st disease flare for the RR population will be calculated as follows:

Duration of ADA exposure after 1st disease flare = last adalimumab dose date in the study after re-randomization due to 1st disease flare – first dose date of adalimumab after re-randomization due to 1st disease flare + (max.*) 14 days

*cutting before first dose of study drug in Study M10-870, if applicable

The overall adalimumab exposure (regardless of double-blind or open-label treatment or if it was rescue therapy after disease flare) will be summarized for the safety population. The duration of overall exposure will be calculated as follows:

- Subjects who are randomized to placebo at Week 8 and who have not been re-randomized due to a disease flare:
 - Overall ADA exposure = Duration of induction-exposure
- Subjects who are randomized to placebo at Week 8 and are re-randomized due to at least one disease flare during maintenance:

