11.2 Analysis of Adverse Events

Treatment-emergent AEs are defined as events with an onset date after the first dose of the study medication (i.e., on/after Rx Day 1) and with an onset date no more than 70 days after the last dose of the study medication. For subjects who roll over into the extension Study M10-870, the window ends prior to first dose date in Study M10-870 (but not more

than 70 days after the last non-missing injection date in Study M11-290). AEs with missing or unknown severity will be categorized as severe. AEs with missing or unknown relationship to study drug will be categorized as 'Reasonable Possibility' of being related to study drug. AEs that are reported more than 70 days after last dose of study drug will be excluded from the treatment-emergent AE summaries; however, they will be included in a separate AE data listing.

Separate Adverse Event Overview tables of number and percentage of subjects in the safety population with treatment-emergent AEs and events per 100 patient-years of induction-exposure and maintenance-exposure (as defined in Section 9.1) will be provided for events during induction period and events during maintenance period (prior to rerandomization due to disease flare if applicable), respectively. AEs that occur after the first dose of study drug in the maintenance period should not be considered treatment-emergent in the induction period, even if they occurred within 70 days of the last dose of study drug in the induction period.

The Adverse Event Overview tables for treatment-emergent AEs in maintenance period (prior to re-randomization due to disease flare if applicable) will also be provided for the RR population. Additionally, an Adverse Event Overview table of events after rerandomization due to first disease flare per 100 PYs of ADA exposure after first disease flare (as defined in Section 9.1) will be provided for the RR population by treatment groups with vs. without re-induction dose (as defined in Section 5.1).

Additionally, an Adverse Event Overview table of adalimumab-treatment-emergent events (i.e., during any ADA exposure throughout the study) per 100 patient-years of overall ADA exposure (as defined in Section 9.1) for patients in the safety population will be provided.

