AEs will also be summarized and presented using primary MedDRA system organ classes (SOCs) and preferred terms (PTs) according to the version of the MedDRA coding dictionary used to code the AE data. The system organ classes will be presented in

Adalimumab M11-290 – Statistical Analysis Plan Version 3.0 – 08 Aug 2019

alphabetical order and the preferred terms will be presented in alphabetical order within each system organ class.

In addition, a summary of AEs by maximum severity and relationship to study drug will be presented.

A subject who reports more than one AE in different system organ classes will be counted only once in the overall total. A subject who reports two or more different preferred terms which are in the same SOC will be counted only once in the SOC total. A subject who reports more than one AE with the same preferred term will be counted only once for that preferred term using the most extreme incident (i.e., most "severe" for the severity tables and as having a 'Reasonable Possibility' of being related to study drug for the relationship tables).

[figure not shown]
Summaries by subject number and listings will also be provided as appropriate.

An overview of AE categories by type of output is provided below:

[figure not shown]
• Adverse Event Overview

The number and percentage of subjects experiencing treatment-emergent AEs, as well as events per 100 PYs, will be summarized for the following AE categories:

- Any AE
- SAEs
- Severe AEs
- AEs leading to discontinuation of study drug
- AEs rated as possibly related to study drug by the investigator (reasonable possibility)
- SAEs rated as possibly related to study drug by the investigator (reasonable possibility)
- AEs leading to Death
- AEs of special interest (see below)

[figure not shown]
- AEs of special interest include:
 - Infections
 - Serious infections
 - Opportunistic infections excluding oral candidiasis and tuberculosis (TB)
 - o TB (active/latent)
 - Oral candidiasis
 - Legionella infections
 - Parasitic infections
 - Diverticulitis
 - Malignancies
 - o Lymphoma
 - Hepatosplenic T-cell lymphoma (HSTCL)
 - o Leukemia
 - Non-melanoma skin cancer (NMSC)
 - Melanoma
 - Malignancy other than lymphoma, HSTCL, leukemia, NMSC or melanoma
 - Lupus-like reactions and systemic lupus erythematosus
 - Allergic reactions including angioedema/anaphylaxis
 - Stevens-Johnson syndrome
 - Sarcoidosis
 - Vasculitis (cutaneous/non-cutaneous)
 - Demyelinating disorder

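### For children who roll over, SAP 11.2 closes the treatment-emergent window before the Week 52 visit date, so adverse events dated at or after that visit, latent TB above all, miss the M11-290 summary tables

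*SAP*

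**What the plan says.** The protocol (8.1.5, Statistical Analyses of Safety) counts an adverse event as treatment-emergent if it begins on or after the first dose and "within 70 days after the last dose of the study medication". It makes no exception for children who enter the extension.

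SAP 11.2 keeps the 70-day rule in general ("with an onset date no more than 70 days after the last dose of the study medication") but adds a cut: "For subjects who roll over into the extension Study M10-870, the window ends prior to first dose date in Study M10-870". SAP 9.1 fixes when that dose is given: "patients in this study don't receive study drug at Week 52, unless they roll over into Study M10-870", in which case the Week 52 dose is the first M10-870 dose and is recorded in that study.

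Two safety-relevant procedures are scheduled at the same visit:

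- **TB test.** Footnote h of Protocol Table 1 says: "For subjects with a negative TB test at Screening, TB test will be required at Week 52". No other TB test is scheduled after Screening. On reporting, Protocol 5.3.1.1 says: "Any positive TB screen after the subject has started the study, should be reported as an AE". SAP 11.2 lists active and latent TB among the adverse events of special interest.
- **Endoscopy.** For completers, Week 52 is the only scheduled endoscopy after Screening, with biopsy at the investigator's discretion. Protocol 5.3.1.1 continues from "If a diagnosis of colon dysplasia or colon cancer or an infection is discovered during any subsequent endoscopic evaluation" to require that the finding be recorded as an adverse event and the subject discontinued.

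**The concern.** The cut in SAP 11.2 works on the dose date, not the time of day. If the first extension dose is given at the Week 52 visit, everything dated to that visit is outside the M11-290 window, even if it preceded the injection. The visit on which the study schedules its TB re-test is thus excluded from the tables meant to report TB.

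A child with latent TB found at Week 52 can still roll over as far as these documents show, because Protocol 5.3.1.1 requires study drug to be stopped for active TB but not for latent TB alone. Such an event, about a week after an M11-290 dose, would not appear in the special-interest row or the rate per 100 patient-years. A child with the same result who did not roll over would be counted. Ascertainment would then differ by rollover status, and a low count could be misread as a safety finding.

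**Working it through.** **Inputs**

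- Nominal days: SAP 6.0, analysis-window table. Week 52 = Day 365.
- Last scheduled M11-290 injection: Week 51 (Protocol Appendices G and H). No M11-290 injection at the final visit (Protocol 5.1).
- First M10-870 dose for rollovers: Week 52 visit (SAP 9.1).
- Visit window: ±3 days (Protocol 5.1).
- PPD read 48 to 72 hours after placement (Protocol 5.3.1.1).

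**Step 1: reproduce the plan's day count.** With no Day 0, Rx Day = 7 × week + 1. Week 52 gives 7 × 52 + 1 = 365, as in the SAP; the formula matches all 11 nominal days in the table. Week 51 gives 7 × 51 + 1 = 358.

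**Step 2: window ends.**

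- Not rolling over, and under the protocol definition: last dose + 70 = 358 + 70 = Day 428.
- Rolling over (SAP 11.2): min(first M10-870 dose day − 1, last dose + 70) = min(364, 428) = Day 364.

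**Step 3: vary the visit day**, holding the Week 51 dose at Day 358.

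| Week 52 visit | Days since last dose | Rollover window ends | 70-day window ends | Days removed | Visit inside rollover window? | Visit inside 70-day window? |
|---|---|---|---|---|---|---|
| Day 362 | 4 | 361 | 428 | 67 | No | Yes |
| Day 365 | 7 | 364 | 428 | 64 | No | Yes |
| Day 368 | 10 | 367 | 428 | 61 | No | Yes |

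**Step 4: TB test.** A PPD placed on Day 365 is read on Day 367 or 368. Both days are after Day 364 and before Day 428. QuantiFERON blood is listed under the Week 52 visit in Protocol Appendix N, so a result dated to the draw or later also falls outside the rollover window.

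**Step 5: endoscopy.** Dysplasia known before the extension dose calls for discontinuation (Protocol 5.3.1.1 and 5.4.1). Such a child would not be expected to roll over, so the 70-day window applies and the event is counted. Protocol 5.3.1.1 gives the same instruction for an infection found at endoscopy. The event is lost only if the result is reported or dated after rollover.

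**Step 6: would a one-day extension suffice?** Ending the window on the day of the first extension dose (Day 365) captures same-day events. It still misses a PPD dated to its reading on Day 367 or 368, or a later laboratory or pathology report, unless onset is set to the procedure date. Neither document says which date to use for a finding detected by a test.

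**The case against.** The best defence is that the cut is deliberate. SAP 9.1 also ends exposure before the first M10-870 dose, a cut prevents one event being counted in two studies, and Protocol 8.1.5 leaves analysis details to the SAP. That justifies a cut for new events starting after the extension dose. It does not justify dropping events found before that dose or by an M11-290 procedure. Nor is matching events to exposure a consistent principle here: children who do not roll over have a 70-day event window against at most 14 days of added exposure.

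Two further defences help only in part. SAP 6.0 imputes partially missing onset dates in favour of treatment-emergence, but a Week 52 test would normally have a complete date. SAP 11.2 plans listings of all adverse events and of those of special interest, so the events are not hidden; but listings do not correct counts or rates. The separate listing promised there covers only events more than 70 days after the last dose, which these are not.

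Some of the objection stands. A reader might infer that dysplasia found at Week 52 drops out, or that no TB conversion in a rollover could ever be counted. The documents support neither. Known dysplasia leads to discontinuation, which restores the 70-day window, and Week 52 biopsy is optional. A TB test or endoscopy done and dated before the visit day is still counted, as is an earlier unscheduled test. The diary rules, which exclude the endoscopy day and the two days after it, suggest that endoscopy may precede the visit. Whether M10-870 counts these events, or delays dosing until a TB result is known, cannot be checked here.

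**Conclusion.** The point holds in a limited form. For children who roll over, adverse events with onset on or after the Week 52 visit date are excluded from the M11-290 treatment-emergent tables although they meet the protocol definition. The window closes 64 days early on the nominal schedule (61 to 67 across the visit window), and the excluded visit lies 7 days (4 to 10) after the last M11-290 dose. Latent TB is the outcome most clearly affected.

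This assumes that the first extension dose is given at the Week 52 visit, as SAP 9.1 states, and that the recorded onset is the visit date or later. The number of events cannot be derived: the documents give neither a rollover share nor a TB conversion risk. The planned maintenance entry of 57 + about 12 = 69 children is only a planning ceiling on those who could roll over. Some will leave before Week 52, and children with a previous positive TB test or treated TB are exempt from the re-test. It would be wrong to conclude that the tables must show zero latent TB, and no efficacy result is affected. The change is still worth making, because a stated rule removes events of a named special-interest category and the repair is cheap.

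**What to change.** In SAP 11.2, keep the rollover cut for new events that start after the first M10-870 dose, and add:

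1. An adverse event that is a finding of an M11-290 Week 52 procedure (TB test, endoscopy or biopsy, other pre-dose assessment) takes the date of the procedure as its onset date.
2. These events, and events with onset on the Week 52 visit date recorded as before the first M10-870 dose, are treatment-emergent in M11-290 if within 70 days of the last M11-290 dose.
3. They are assigned to the child's maintenance group, or to the post-flare group if the child was re-randomised, and flagged so that M10-870 does not count them again.

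The cost is a short SAP insertion, one programming flag and coordination with the extension study. No dose, test or clinical rule changes.

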Overall ADA exposure = Duration of induction-exposure + (last adalimumab dose date in the study after re-randomization due to 1st disease flare – first dose date of adalimumab after re-randomization due to 1st disease flare + (max.*) 14 days)

*cutting before first dose of study drug in Study M10-870, if applicable

• Subjects who are not randomized to placebo:

Overall ADA exposure = last adalimumab dose date in the study – first dose of adalimumab + (max.*) 14 days.

*cutting before first dose of study drug in Study M10-870, if applicable

[figure not shown]

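### Adverse event rates per 100 patient-years count events to 70 days after the last dose but patient-time to at most 14, so rates are overstated for subjects who stop

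*SAP*

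**What the plan says.** SAP Section 11.2 defines treatment-emergent events as those starting after the first dose and "with an onset date no more than 70 days after the last dose of the study medication". Protocol Section 8.1.5 uses the same 70-day limit. The overview tables then give "events per 100 patient-years of induction-exposure and maintenance-exposure (as defined in Section 9.1".

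Section 9.1 sets the denominators: "Duration of induction-exposure = last induction dose date - first induction dose date + (max.*) 14 days". Maintenance exposure and post-flare adalimumab exposure carry the same limit of at most 14 days.

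The two windows share their early cuts:
- **First maintenance dose.** Section 9.1 stops induction time there. Section 11.2 stops assigning events to induction there, "even if they occurred within 70 days of the last dose of study drug in the induction period".
- **Flare re-randomisation.** Maintenance events are those before it, and maintenance time is limited by "cutting before first dose of study drug after re-randomization due to 1st disease flare, if applicable".
- **First extension-study dose.** It closes both windows.

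Two further tables matter. One reports "events after rerandomization due to first disease flare per 100 PYs of ADA exposure after first disease flare". The other reports "adalimumab-treatment-emergent events (i.e., during any ADA exposure throughout the study", with a denominator that, for subjects not randomised to placebo, is "last adalimumab dose date in the study – first dose of adalimumab + (max.*) 14 days".

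**The concern.** A rate needs events and time taken from the same window. Here, someone who stops without starting a next period can contribute events from days 15 to 70 after the last dose, but no patient-time for those days. These events will be in the data: the opening sentence of Protocol Section 6.1.4 provides for collecting all adverse events until 70 days after stopping.

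The induction tables are the most exposed, because Week 8 non-responders are discontinued by design (SAP Section 4.2). The inflation then depends on response: at equal true risk, the dose group with fewer responders would show the higher rate. Rates per 100 patient-years appear in the overview rows and in the system organ class and preferred term tables.

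**Working it through.** **Plan's own figure.** The documents state no adverse event rate or patient-year total. The one stated figure that uses the driver, Week 8 response, is the sample size in SAP Section 4.3: 93 × 0.75 − 12 = 57.75, against 57 planned in the adalimumab maintenance groups. The 75% input is therefore consistent.

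**Inputs.** Last induction dose at Week 6, day 42 (SAP Section 4.2). Week 8 dose not part of induction (Section 9.1). Event tail 70 days (Section 11.2). Time tail at most 14 days (Section 9.1). Non-response s = 0.25 (Section 4.3). The ratio k is not in the documents; I assume 0.25 to 1.5.

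**Induction, per subject**

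| Subject | Days counting events | Days counted as time | Ratio |
|---|---|---|---|
| Responder, cut at Week 8 | 56 | 56 | 1.00 |
| Non-responder, last dose Week 6 | 42 + 70 = 112 | 42 + 14 = 56 | 2.00 |
| Stops, last dose Week 4 | 28 + 70 = 98 | 28 + 14 = 42 | 2.33 |
| Stops, last dose Week 2 | 14 + 70 = 84 | 14 + 14 = 28 | 3.00 |

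**Induction, per group.** If everyone receives the Week 6 dose, the reported rate divided by the on-drug rate is (56 + s·k·56)/56 = 1 + s·k. At s = 0.25:
- k = 0.25: 1.0625
- k = 0.5: 1.125
- k = 1: 1.25
- k = 1.5: 1.375

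Incomplete follow-up lowers these values and stops before Week 6 raise them. For 93 subjects, counted time is 93 × 56/365.25 = 14.26 patient-years. The uncounted tail is 93 × 0.25 × 56/365.25 = 3.56, so events are counted over 17.82. Against that matched 70-day time the overstatement is 17.82/14.26 = 1.25, whatever k is.

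**Between dose groups.** Assume 79% response in 46 high-dose and 69% in 31 standard-dose subjects; pooled, (46 × 0.79 + 31 × 0.69)/77 = 0.750. The spurious standard-to-high rate ratio is:
- k = 0.5: 1.155/1.105 = 1.045
- k = 1: 1.31/1.21 = 1.083

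**Maintenance, per subject**
- Last dose at Week 26: (126 + 70)/(126 + 14) = 196/140 = 1.40.
- Completer not rolling over, last dose Week 51: (301 + 70)/(301 + 14) = 371/315 = 1.18.
- Completer rolling over at Week 52: 308/308 = 1.00.

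If 10% stop at Week 26 (assumed), with no flares and k = 1, the group overstatement is 5.6/291.2 = 1.9% when all completers roll over and 56/297.5 = 18.8% when none do. These are outer bounds, not forecasts.

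**Does matching to 70 days remove the dose effect?** The matched rate relative to the on-drug rate is (1 + s·k)/(1 + s). At k = 0.5 and the same assumed responses, the ratio is (1.155/1.31)/(1.105/1.21) = 0.882/0.913 = 0.965. It equals 1 only when k = 1.

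**The case against.** The tables are descriptive. No test, threshold or decision rests on the rates, the error is towards more reported harm, and subject numbers and percentages stand beside each rate. That is correct, and it limits the importance of the point. It does not justify a rate whose two parts cover different time.

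The dose-group effect is small and rests on assumptions. The documents give only a pooled 75% response and nothing on k. With 7.05 and 4.75 counted patient-years and an assumed 300 events per 100 patient-years, there would be about 21 and 14 events, and 95% limits on the ratio of roughly a factor of 2 either way. This stands: a ratio of 1.05 to 1.08 would not change how such small groups are read. It remains a systematic error that is cheap to avoid.

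Restricting events to 14 days as the only rate would leave late events out of the rate while the count in the same row kept them, and would depart from the protocol's definition. This also stands, and it determines the order of the fix.

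One could argue that wording about events during the induction period already closes the tail. The carve-out for responders in Section 11.2 answers this: it would be unnecessary if the 70-day tail did not operate in induction, and no equivalent cut exists for non-responders.

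**Conclusion.** The mismatch is explicit for the induction, maintenance and post-flare rate tables, and should be corrected. It affects only subjects who stop, and only event types that can start after stopping. Injection site reactions and events leading to discontinuation of study drug hardly move. In induction the overstatement is 1 + s·k: +12.5% to +25% at 75% response for k between 0.5 and 1, given complete follow-up and a Week 6 dose for everyone. The maintenance size depends mainly on roll-over, and its direction between doses cannot be predicted.

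A reader might infer more than the documents support:
- **That counts and percentages are wrong too.** They have no patient-time denominator, so this mismatch does not touch them.
- **That one dose will be made to look less safe.** Group-specific response and k are not given, so the ratio is only an illustration.
- **That the overall-adalimumab table has the same fault.** Its event tail is not stated, so it is unclear rather than shown to be mismatched.

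**What to change.** 1. Keep the protocol's 70-day treatment-emergent definition. For every adverse event rate, run patient-time to the earliest of 70 days after the last dose, first dose of the next period, first dose after flare re-randomisation, first extension-study dose, or end of follow-up.
2. For comparing dose groups, add a separately labelled on-treatment rate: events to 14 days after the last dose over the existing Section 9.1 exposure. It is needed because the 70-day rate still varies with the share of stoppers unless k = 1.
3. State the event window for the overall-adalimumab table and match its denominator to it.
4. Keep the 14-day definition for the exposure tables.

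The cost is a revised SAP definition and a small programming change, with one extra rate to produce. No new data and no patient burden are involved. Reported rates will be lower; for induction at 75% response the matched rate is the current one divided by 1.25, a 20% reduction.
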